### **21.3. Statistical Analyses**

All analyses will be based on the intent-to-treat principle using the FAS, including only events adjudicated by the Clinical Events Adjudication Committee (CEC). The primary hypothesis will be tested using a Cox proportional hazards model with a factor for the treatment group. The time to the first event was used in the model when there were multiple events of the same type. P values and Confidence Intervals (CI) for the Hazard Ratio will be obtained according to the Wald statistic. The following statistics, in addition to HR with CI will be also presented in the summary tables of these analyses: the number of patients with event and Kaplan-Meier estimates of the event rate per treatment group calculated at EoT. Kaplan-Meier estimates of the cumulative proportion of patients with primary endpoint events will be calculated and plotted.

The potential impact of loss to follow-up will be evaluated by the sensitivity analysis.

A Cox proportional hazards model will be used to assess differences between study groups in the rate of primary endpoint under the following three scenarios: (1) all patients will be thought to experience primary endpoint event when the final disposition for the event adjudication is not determined. (2) only patients in the empirical bypass arm will be thought to experience primary endpoint event when the final disposition for the event adjudication is not determined. (3) only patients in the multimodal neuronavigation guiding bypass arm will be thought to experience primary endpoint event when the final disposition for the event adjudication is not determined. These results under the three scenarios will be compared with the result under the scenario in which all patients will be not thought to have primary endpoint event when the final disposition for the event adjudication is not determined. However, the primary analysis result will be reported in patients who are censored not to have the event occurrence when the final disposition for the event adjudication is not determined.

The analysis of and the secondary efficacy variable for the test of multimodal neuronavigation guiding bypass against empirical bypass will comprise the confirmatory analysis. No multiplicity adjustment will be made in all analysis including a confirmatory testing (subgroup analysis).

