#### Risk of Stroke or Hemorrhage for MMD

The greatest concern for MMD is the risk of subsequent stroke or hemorrhage even with surgical revascularization and regular medical therapy. A retrospective, single-center, cohort study showed most subsequent ischemic events appeared in the first 2 years after surgery. The Kaplan-Meier estimated stroke risk was 10.1% and 12.7% in the first 2 years and 5 years after surgery for all patients treated with surgical revascularization, approximated 10.1% incidence of mortality or TIA or stroke at 1 year after surgery in 802 patients with the MMD. Incidence of rebleeding range from 12.5~20% of patients with onset hemorrhage symptom who underwent revascularization surgery, while with the conservation treatment the rebleeding estimated occurrence of 6.8–65%.

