### **Surgical treatment for MMD**

Revascularization surgery has played an important role for treatment of MMD. Several general methods of revascularization had been used: direct, indirect and combined techniques. Two large studies with long term follow-up showed a good safety profile for surgical treatment. During the postoperative 30 days the risk of stroke is highest (approximately 4% per hemisphere); and after the first month, the risk decreases fairly. It is reported that patients have a 96% probability of remaining stroke-free over the subsequent 5 years. Patients with MMD have a higher risk of perioperative ischemic events. The complications associated with the treatment include stroke, infection, and intracranial hemorrhage.

Currently, there are no reports on the MMD research that refer to the criteria of receptor vessel selection in bypass surgery for MMD. Surgeons usually performed superficial temporal artery to MCA (STA–MCA) anastomosis. Sometimes when patients have severe ischemia in ACA area the STA can also be anastomosed to the branch of the ACA. So precisely choosing receptor vessel remains uncertain. As the imaging advanced, ASL can be used as a perfusion method to detect the ischemia area and intraoperative ICG angiography using Flow800 software can be used to reflect the lower flow velocity and superficial perfusion. Guided by this two imaging data, we try to precisely find the receptor vessel.

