## **15. Leading Phase of Trial for Site Selection**

Candidate sites for trial will be initially identified based on hospital grades, the intervention experience, and the volume of revascularization surgery cases. It will take three months before the trial kickoff for the steering committee to assess site research capability and commitment to the study. The center meeting the following criteria will be enrolled into the trial: ① at least 5 cases will be recruited within the leading phase; ② the rate of perioperative complications should be not more than 15% (stroke or death).

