### **21.1. Sample size estimates**

Because this trial is a prospective, exploratory, randomized controlled trial, there is no previous data for multimodal neuronavigation guiding precise bypass procedure, the sample size for this trial can't be calculated from the formula. Finally, 100 patients are randomized (1:1) to two groups, 50 of them will undergo direct bypass guided by multimodal neuronavigation, while others will undergo empirical direct bypass procedure.

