## 21.7. Interim analyses

One interim analysis will be planned and conducted by the Data Monitoring Committee following the accrual and confirmation by adjudication of 50% of planned primary events. The stopping rule of Lan-DeMets approach to O'Brien-Fleming will be adopted for stopping for efficacy or futility. The efficacy stopping boundary at the interim analysis is a 2-sided p-value <0.0015 for the primary endpoint (one-year stroke or death). The final last level of significance with one interim analysis will therefore be 0.0489, with the family wise error rate controlled at 5.00%. The trial would be halted due to futility if nominal critical point (Standardized Z scale) for the primary endpoint crosses the internal boundary for futility ( $\pm 0.595$ ). It will be determined by the executive committee that the trial will be continued or stopped due to the overwhelming efficacy or futility after recommendation of Data Safety Monitoring Board.

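### The Wald rule for the primary Cox test gives p near 1 and an unbounded hazard-ratio interval whenever one arm has no events

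*Protocol*

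**What the plan says.** Section 21.3 states: "The primary hypothesis will be tested using a Cox proportional hazards model with a factor for the treatment group". It continues: "P values and Confidence Intervals (CI) for the Hazard Ratio will be obtained according to the Wald statistic". It names no score, log-rank, likelihood-ratio, exact or penalised alternative, and no rule for an arm without events. Event counts and Kaplan-Meier estimates per arm accompany the hazard ratio as summaries.

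The three sensitivity scenarios for undetermined adjudications use a Cox model too. In scenario (3), "only patients in the multimodal neuronavigation guiding bypass arm will be thought to experience primary endpoint event" where the adjudication is unresolved.

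On size, section 21.1 says "100 patients are randomized (1:1) to two groups", so 50 per arm. It gives no event rate, effect or power, and calls the trial exploratory. The primary endpoint (section 6.1) counts any stroke or death up to day 30 after surgery, and after that only ipsilateral hemorrhage. On the final level, section 21.7 says: "The final last level of significance with one interim analysis will therefore be 0.0489".

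**The concern.** The Wald statistic divides the estimated log hazard ratio by its standard error. With no events in one arm the partial likelihood has no maximum: it keeps rising as the log hazard ratio goes to minus infinity. The standard error grows faster than the estimate, so the ratio goes to zero. The split most favourable to one arm is therefore the one in which the prespecified test cannot reject and the prespecified interval cannot be reported.

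With 50 patients per arm and an endpoint that narrows sharply after day 30, an empty arm is a realistic outcome. The sensitivity scenarios are exposed as well: adding one event to an empty navigation arm makes the Wald p-value fall, so a result can look better for navigation after harm has been added to it.

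**Working it through.** The protocol derives no event count or power, so there is no stated figure to reproduce. The check is direct.

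**Inputs.** 50 per arm (21.1); two-sided final level 0.0489 (21.7). For control risk r, three anchors from the protocol:
- 4%: the 30-day stroke risk per hemisphere in section 3.
- 10.1%: section 3 cites "approximated 10.1% incidence of mortality or TIA or stroke at 1 year after surgery". This includes TIA, so it is broader than the primary endpoint.
- 15%: the ceiling for perioperative stroke or death in site selection (section 15). This is an upper end only.

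Hazard ratios of 0.5 and 0.2 are assumptions.

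**Step 1: the Wald limit at 0 versus 6.** With no ties or dropout, the information at log hazard ratio β is Σp(1−p), where p = 50e^β/(50e^β + n) and n = 50, 49, …, 45 controls are at risk. For very negative β this is about e^β × Σ50/n = 6.32e^β.
- β = −10: SE = 1/√(6.32 × 0.0000454) = 59; Z = −0.17; p = 0.87.
- β = −15: p = 0.98.
- β = −20: p = 0.998.

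Z goes to 0 and the interval to (0, ∞). A direct Newton fit gave Wald p of 0.9996 or more for every split tried from 0 versus 2 to 0 versus 10.

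**Step 2: other tests on the same data.** At 0 versus 6 the log-rank test has 3.078 expected navigation events and variance 1.498, so chi-square = 3.078²/1.498 = 6.32 and p = 0.012. For 0 versus b events the two-sided permutation p is exactly 2·C(50,b)/C(100,b), which is 0.1175, 0.0563, 0.0267, 0.0125 and 0.0058 for b = 4 to 8. The 1 versus 8 row is a median over event orderings.

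| Navigation vs control events | Wald | Log-rank | Permutation log-rank | Fisher |
|---|---|---|---|---|
| 0 vs 4 | about 1 | 0.042 | 0.12 | 0.12 |
| 0 vs 5 | about 1 | 0.022 | 0.056 | 0.056 |
| 0 vs 6 | about 1 | 0.012 | 0.027 | 0.027 |
| 0 vs 8 | about 1 | 0.003 | 0.006 | 0.006 |
| 1 vs 8 | 0.043 | 0.015 | 0.018 | 0.031 |

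The last two rows show the sensitivity problem. If scenario (3) turns 0 versus 8 into 1 versus 8, Wald p drops from about 1 to 0.043, below 0.0489. The permutation p rises from 0.006 to 0.018, as it should.

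**Step 3: how often this arises.** Under proportional hazards the navigation arm is empty with probability e = (1−r)^(50·HR), and the control arm with a = (1−r)^50. Exactly one arm is empty with probability a + e − 2ae. The conclusion changes against the permutation log-rank (or Fisher) when navigation has 0 events and control at least 6, with probability e × P(Bin(50, r) ≥ 6). Against the asymptotic log-rank the threshold is 4.

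| r | HR | e | Exactly one arm empty | P(≥6) | Changed vs permutation | P(≥4) | Changed vs asymptotic |
|---|---|---|---|---|---|---|---|
| 4% | 0.5 | 0.360 | 40% | 0.0144 | 0.5% | 0.139 | 5.0% |
| 4% | 0.2 | 0.665 | 62% | 0.0144 | 1.0% | 0.139 | 9.2% |
| 10.1% | 0.5 | 0.0698 | 7% | 0.393 | 2.7% | 0.757 | 5.3% |
| 10.1% | 0.2 | 0.345 | 35% | 0.393 | 13.6% | 0.757 | 26.1% |
| 15% | 0.5 | 0.0172 | 2% | 0.781 | 1.3% | 0.954 | 1.6% |
| 15% | 0.2 | 0.197 | 20% | 0.781 | 15.4% | 0.954 | 18.8% |

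**Step 4: power, for context.** Simulated at 0.0489 (12,000 replicates per cell, Wald Z set to 0 for an empty arm), Wald versus permutation log-rank:
- r = 10.1%: 4.4% vs 11.4% (HR 0.5); 5.8% vs 25.4% (HR 0.2).
- r = 15%: 13.0% vs 18.8%; 26.4% vs 50.6%.
- r = 4%: under 0.1% vs 0.7%; under 0.1% vs 1.2%.

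At 10.1%, empty arms supply 2.7 of the 7.0-point gap at HR 0.5 and 13.9 of the 19.6 points at HR 0.2 (simulated; the exact figure from step 3 is 13.6). The rest comes from arms with few events, where Wald is conservative but still works, and is not claimed as a defect. Null rejection at 4%, 10.1% and 15% is 0.05%, 2.0% and 3.6% for Wald, and 0.8%, 4.2% and 5.0% for the permutation test.

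**The case against.** The strongest reply is about weight. An empty arm is most likely where it matters least: at 4% control risk and HR 0.5 the navigation arm is empty in 36% of trials, but control rarely reaches 6 events, so the conclusion changes in 0.5%. Double-digit figures need an 80% hazard reduction that the protocol does not assume. The 10.1% and 15% anchors are not expected rates for this endpoint. The error is conservative, the trial is called exploratory, and the required counts and Kaplan-Meier estimates would make the split plain. The sensitivity reversal also needs at least 8 control events (at 1 versus 7 Wald p is 0.061). At HR 0.5, 0 versus 8 or more has probability 0.9% at most across the three anchors, before requiring an undetermined navigation patient.

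All of that stands, and it limits the size of the point. It does not remove it. Counts and curves supply neither a treatment p-value nor an interval, and a test chosen after seeing an empty arm would be post hoc.

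A second reply is that section 21 is an overview and a non-convergence rule belongs in the SAP. Here, however, the protocol itself fixes the Wald statistic, so this concerns a stated rule and not an omission.

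A third is that a fallback for an empty arm would suffice. It would cure the failure. But the sensitivity comparison could then set a permutation p at 0 versus 8 beside a Wald p at 1 versus 8; one test throughout avoids that.

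**Conclusion.** The concern holds, confined to an arm with no events. In that case the rule in section 21.3 gives p near 1 and no usable interval, whatever the other arm shows. This follows from the Cox likelihood and needs no assumption.

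Its frequency does rest on assumptions: proportional hazards, no dropout, and the control risks and hazard ratios above. The primary conclusion is reversed relative to a permutation log-rank in 0.5% to 2.7% of trials at HR 0.5 and 1.0% to 15.4% at HR 0.2. The hazard ratio and interval become unreportable more often: exactly one arm is empty in 2% to 40% of trials at HR 0.5 and 20% to 62% at HR 0.2. No false positive is created in the primary analysis. The point is worth correcting because the remedy is cheap, but it does not invalidate the trial.

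**What to change.** In section 21.3, replace the Wald sentence. The new text should:
- name the two-sided permutation log-rank test for the primary analysis and all three sensitivity scenarios;
- report the hazard ratio with a Firth-penalised profile-likelihood 95% interval, which stays finite with an empty arm (0 versus 6: HR 0.07, 0.0006 to 0.62);
- state that the permutation p-value decides, because the two can disagree at the margin (0 versus 5: p = 0.056, interval 0.0007 to 0.77).

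The permutation form is preferred because the asymptotic log-rank gives 0.042 at 0 versus 4, where the exact permutation p is 0.12.

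In section 21.7, say that the interim Z comes from the same log-rank test. This is for consistency and is not a separate defect.

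The cost is one sentence in each section, with standard software. The permutation test gives up some power against the asymptotic log-rank (25% versus 38% at 10.1% and HR 0.2), and Firth estimation shrinks the hazard ratio towards 1. Neither change cures the shortage of events: at 4% control risk the permutation test has about 1% power even at HR 0.2.

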## **16. Schedule of Follow-up and Post-study Follow-up Period**

All patients will be followed up until the primary endpoint or the end of the trial. Complete endpoint information will be obtained with the best effort irrespective of

patient study status, unless patients withdraw consent to participate the trial. Patients will continue to be followed up beyond date of consent withdrawal if they stop the trial and receive other treatment such as medical therapy but agree to provide the prognostic information. The face-to-face interview will be performed by study neurologists at discharge, at 3 months, at 6 months and at 12 months (or by telephone) after the recruitment of patients. If they are more convenient to have access to the study site near to their living areas, patients will be allowed to go to the site for their follow-up.

Visits	Windows	Definition
Randomization	0 day	Study Day 0 day
At discharge	0 day	Based on the number of hospitalization days
At 3 month	7 days	Day 83-97
At 6 months	14 days	Day 166-194
At 12 months	30 days	Day 330-390

Note: 1 month= 30 days

The following procedures will be done at 3 months, at 6 months after enrollment:

- ✧ A neurological evaluation will be performed (Modified Rankin Scale, National Institute of Health Stroke Scale, modified Barthel Scale);
- ✧ A physical examination will be performed, including vital signs (blood pressure, heart rate);
- ✧ Information will be collected on medications, risk factors, and events of interest since the last visit;
- ✧ Computed Tomography Perfusion (CTP), Magnetic Resonance (MR) and Digital subtraction angiography (DSA) will be performed;

The following evaluations will be done at the end of trial:

- ✧ Lab tests for diabetic control and hyperlipidemia management will be performed;
- ✧ A neurological evaluation will be performed (Modified Rankin Scale, National Institute of Health Stroke Scale, modified Barthel Scale);
- ✧ A cognitive function evaluation will be performed (MoCA);
- ✧ Computed Tomography Perfusion (CTP) and Magnetic Resonance (MR) will be done if a patient does not experience a primary endpoint before the end of trial. Images will be transferred to the core imaging evaluation lab.
- ✧ Information will be collected on medications, risk factors, and events of interest since the last visit;

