### **21.2. Description of analysis sets**

All patients who have been randomized to study treatment will be included irrespective of their protocol adherence and continued participation in the study. Patients will be analyzed based on the initial treatment assignment irrespective of whether the event occurred before or following discontinuation of study medication. Patients who withdraw consent to participate in the study will be included up to the date of their study termination except for vital status known through public records (for use in the analysis of all cause death). All efficacy variables will be analyzed using the full analysis set (FAS).

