## 21.8. Censoring

Patients who have not had the event(s) in question will be censored at the earliest of EoT visit and the last study contact when all components of the endpoint in question were assessed. Lost patients in whom we cannot accurately determine if the primary endpoint occurred will be censored at the last contact date at which the patient was known to be free from a primary endpoint.

If the study is stopped early at the interim analysis, the mentioned-above censoring rule will apply. When the trial is determined to be stopped, all patients who have not completed the treatment period will be required for a EoT visit as soon as possible.

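### The sensitivity analysis announced for loss to follow-up is triggered only by undetermined adjudication, so as written it need not respond to lost patients; the rules for endpoint data after withdrawal also need reconciling

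*Protocol*

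**What the plan says.** **Sensitivity analysis.** Section 21.3 gives the aim: "The potential impact of loss to follow-up will be evaluated by the sensitivity analysis". It then lists three Cox analyses. In scenario 1, "all patients will be thought to experience primary endpoint event when the final disposition for the event adjudication is not determined". Scenarios 2 and 3 do the same for the empirical arm only and for the guided arm only. The comparison scenario counts none of these patients as having an event, and the primary analysis follows it: "the primary analysis result will be reported in patients who are censored not to have the event occurrence". All four rest on the same condition, an adjudication without a final disposition.

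**Lost patients.** Section 21.8 has its own rule: "Lost patients in whom we cannot accurately determine if the primary endpoint occurred will be censored at the last contact date", meaning the last contact at which they were known to be free of a primary endpoint. No scenario in 21.3 refers to this rule or names lost patients.

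**Withdrawal.** Section 16 says: "Patients will continue to be followed up beyond date of consent withdrawal if they stop the trial and receive other treatment", provided that they agree to supply outcome information. Section 21.2 says that patients who withdraw consent "will be included up to the date of their study termination except for vital status known through public records", the exception being for the analysis of all-cause death.

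**The concern.** The declared aim and the rule do not match. Under section 17, adjudication starts when a patient develops a possible neurological event and the site prepares a packet. A patient who simply stops attending produces no packet, so no disposition can be left undetermined. Applied to the letter, the scenarios test the effect of unfinished adjudication and not of loss to follow-up.

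The trial could then report that three sensitivity analyses agreed with the primary result and call it robust to loss, although loss was not varied. With 100 patients and few expected events, a handful of lost patients could matter.

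The withdrawal rules raise a related question. Non-fatal strokes within 30 days and later ipsilateral hemorrhages are components of the primary endpoint. If they are collected with the patient's agreement after withdrawal but fall outside the analysis, that sits badly with the intent-to-treat statement in section 21.3.

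**Working it through.** **Step 1. What is fixed in the protocol.** 100 patients randomized 1:1, so 100/2 = 50 per arm (section 21.1). Cox model with a treatment factor and Wald inference (section 21.3). Horizon of 12 months (section 4). No loss rate, event rate by arm or effect size is stated, so there is no figure of the plan to reproduce.

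**Step 2. Scale of the event count.** Section 3 gives about 4% stroke per hemisphere in the first 30 days, and 10.1% at one year for a broader outcome that includes TIA. For 100 patients, 0.04 × 100 = 4 and 0.101 × 100 = 10.1. Neither outcome is the primary endpoint. They only suggest an order of roughly 4 to 10 events.

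**Step 3. Constructed data (assumptions).** 5 events in the empirical arm and 2 in the guided arm, all in the first two weeks; 1, 3 or 5 patients lost per arm from day 60 on; everyone else censored at day 360; no pending adjudications. With coefficient b and standard error SE, HR = exp(b), 95% CI = exp(b ± 1.96 SE), and the p value comes from b/SE (Efron ties).

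**Step 4. Literal rule.** With no pending adjudication, nothing is imputed in any scenario. HR is 0.39 (0.08 to 2.03), p = 0.27, in all four scenarios, whether 1, 3 or 5 patients per arm are lost.

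**Step 5. Scenarios also act on lost patients, event at last contact.** With 3 lost per arm, the counts (empirical vs guided) become 5 + 3 = 8 vs 2 if the empirical arm is imputed, 5 vs 2 + 3 = 5 if the guided arm is imputed, and 8 vs 5 if both are.

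| Lost per arm | None imputed | Both arms | Empirical only | Guided only |
|---|---|---|---|---|
| 1 | 0.39 (p = 0.27) | 0.49 (p = 0.31) | 0.33 (p = 0.17) | 0.59 (p = 0.46) |
| 3 | 0.39 (p = 0.27) | 0.60 (p = 0.37) | 0.24 (p = 0.073) | 0.96 (p = 0.95) |
| 5 | 0.39 (p = 0.27) | 0.66 (p = 0.41) | 0.19 (p = 0.034) | 1.34 (p = 0.62) |

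**Step 6. A second assumed split, 8 vs 2 events.** The literal rule gives HR 0.24, p = 0.072, throughout. With 5 lost per arm and the scenarios acting on them, HR runs from 0.14 (p = 0.010) to 0.81 (p = 0.68).

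**Step 7. Withdrawal rules side by side.** Section 16 permits collection of outcome data beyond the date of consent withdrawal. Section 21.2 ends inclusion at study termination, a date it does not define, and keeps only vital status after it. If termination means withdrawal, non-fatal endpoint data are collected and not analysed. If it means the end of the agreed follow-up, the two sections are compatible. The text does not say which applies.

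**The case against.** The strongest reply is that lost patients were meant to be covered. The scenarios come directly after the sentence on loss to follow-up and look like its content. Section 21.8 describes lost patients as those whose primary endpoint status cannot be determined and censors them, which is also how 21.3 treats the undetermined group. Imputing in all patients, then in one arm, then in the other, is what one would write for missing outcomes. This stands as a possible intention, so a reader who infers that loss will certainly go untested goes further than the text allows. It does not rescue the wording, because two analysts could run different analyses from it.

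A reader might also infer that lost patients are carried as event-free to 12 months. They are not: section 21.8 removes them from the risk set at last contact. The accurate statement is that, on the literal reading, they are never imputed an event.

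Nor does the protocol show that all data after withdrawal are discarded. Vital status is kept for all-cause death, and study termination is not tied to the withdrawal date.

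Section 21 calls itself an overview and refers to the SAP, which is not at hand, for complete details. The exact definition of the undetermined group could be settled there. But the protocol itself fixes both the aim and the trigger, and these do not match.

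Finally, this is a sensitivity analysis in a trial that section 21.1 calls exploratory, and the primary estimate does not depend on it.

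**Conclusion.** The point holds in a limited form. Section 21.3 sets an aim, loss to follow-up, that its trigger, undetermined adjudication, does not serve as written. On the literal reading the scenarios cannot respond to patients lost without a reported event; on the generous reading the trigger is ambiguous. In the 5 vs 2 example the difference is between a constant HR of 0.39 and a range of 0.24 to 0.96 with 3 lost per arm.

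The event splits, the numbers lost, their timing and the absence of pending adjudications are all assumptions. The range is also an extreme bound. After day 30 only ipsilateral hemorrhage counts toward the primary endpoint, so treating every later loss as an event is deliberately severe.

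Sections 16 and 21.2 are not shown to contradict each other on every reading, but they leave open whether non-fatal endpoint data given with agreement after withdrawal enter the analysis. They should be reconciled.

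**What to change.** 1. **Section 21.3.** Apply scenarios 1 to 3 to every patient without a primary event whose follow-up ends before the 12-month window (day 330 in section 16), as well as to those with undetermined adjudication. State the date given to the imputed event, for example the last contact. Leave out patients whose follow-up ended through a known death that is not a primary event, or because the whole trial closed early; they are not lost. Say in the text that the scenarios are extreme bounds, because only ipsilateral hemorrhage counts after day 30.

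2. **Sections 16 and 21.2.** Define study termination. State that endpoint data, including non-fatal events, given with agreement after withdrawal of consent are included in the intent-to-treat analysis. Say whether vital status from public records also feeds the primary composite within 30 days.

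The cost is a few sentences and a little more analysis, with no new data collection. The downside is a wider sensitivity range, which is the information that the analysis is meant to give.

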## **5. Study Plan and Procedure**

### **Study Design and Flow Chart**

This will be an investigator-initiated and **Phase III single center trial** in which patients with TIA, stroke or other ischemic symptoms prior to enrollment that is attributed to progressive stenosis or occlusion in the terminal portion of the internal carotid artery and/or the initial portion of the anterior or middle cerebral arteries unilaterally or bilaterally and formation of abnormal collateral networks (moyamoya vessels) at the base of the brain will be randomized (1:1) to:

Direct bypass surgery guided by multimodal neuronavigation. Combine local cerebral blood flow velocity and superficial perfusion assessed by Flow800 software that implements conventional ICG fluorescence angiography and deep perfusion assessed by multimodal MR (structure combined with perfusion sequence) to determine the recipient vessel.

OR

Empirical direct bypass surgery.

The evidence-based program of risk factor management will be administered to all patients by the study neurosurgeon at each site at regularly scheduled times throughout the study.

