## **6. Study Endpoints**

### **6.1. Primary Endpoint**

All strokes & death within 30 days post-surgery and ipsilateral hemorrhage afterwards

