### **6.2. Clinical Secondary Endpoint**

- All kinds of adverse events related to surgery within 30 days
- Infarctions on the contralateral side within 1 year of randomization
- Transient ischemic attack on the surgically treated side within 1 year of randomization

- The changes from baseline in CBF measured by ASL at 7 days, 3 months, 6 months, 12 months or end of trial
- The changes from baseline in modified Rankin Scale (mRS) at 7 days, 3 months, 6 months, 12 months or end of trial
- The changes from baseline in National Institute of Health Stroke Scale (NIHSS) at 7 days, 3 months, 6 months, 12 months end of trial
- The changes from baseline in modified Barthel Scale at 7 days, 3 months, 6 months, 12 months or end of trial

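### Section 21.3 makes a secondary efficacy variable confirmatory and rules out multiplicity adjustment, while 21.1 calls the trial exploratory and the 5.00% error rate in 21.7 covers only the primary endpoint

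*Protocol*

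**What the plan says.** Section 21.3 ends with two sentences that fix the status of the tests. The first reads: "The analysis of and the secondary efficacy variable for the test of multimodal neuronavigation guiding bypass against empirical bypass will comprise the confirmatory analysis". Words seem to be missing near its start. The second reads: "No multiplicity adjustment will be made in all analysis including a confirmatory testing (subgroup analysis"), and the parenthesis closes there.

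Section 21.1 gives the reason for having no sample-size formula in a sentence that opens: "Because this trial is a prospective, exploratory, randomized controlled trial". The size is set at 100 patients, 50 per arm, without a calculation.

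Section 21.7 sets one interim look at half of the planned primary events, with an efficacy boundary of 0.0015 two-sided and a final level of 0.0489, "with the family wise error rate controlled at 5.00"%. The boundary is tied to the primary endpoint.

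Section 6.2 has a heading in the singular, lists seven secondary endpoints and ranks none of them. Section 21.5 lists ten subgroup factors and does not call them confirmatory.

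**The concern.** Leaving secondary analyses unadjusted is acceptable when they are labelled exploratory. Here the protocol does the reverse: it calls a secondary test confirmatory and expressly declines to control its error. It also does not say which endpoint of 6.2 is meant, or whether all of them are, so the size of the confirmatory set cannot be read from the text.

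If the text is followed, one nominally significant secondary result from a 100-patient trial of uncalculated size could be reported as confirmatory evidence for guided bypass, with the protocol cited in support. That sits badly with 21.1. It also invites the mistaken belief that the 5.00% in 21.7 protects such a claim.

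**Working it through.** **The plan's own figure.** Inputs from 21.7: interim at information fraction 0.5, two-sided 0.0015; final level 0.0489. With correlation √0.5 between the two looks and futility ignored, the error rate is P(|Z1| ≥ z(0.0015/2) or |Z2| ≥ z(0.0489/2)) = 4.93%. The plan states 5.00%. The figure is not reproduced exactly, but it stays below 5%, and the small mismatch is not part of this point. What matters here is coverage: this calculation contains two looks at one endpoint and no secondary test.

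**The text with its gap filled.** The likely missing words are a mention of the primary variable. With them restored, the confirmatory set is primary plus secondary. The next sentence still withholds adjustment, so the secondary variable remains confirmatory and uncontrolled. Deleting the parenthesis about subgroups does not change this either, because the rule already covers all analyses, including confirmatory ones.

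**Size under the two readings of the singular.** Assumptions: no true effect, one test per endpoint, and 0.05 two-sided per secondary test, since the protocol gives no level for these.

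- One secondary variable alongside the primary endpoint at its final level of 0.0489, independent: 1 − (1 − 0.0489)(1 − 0.05) = 1 − 0.9511 × 0.95 = 0.096, about 9.6%. Using the claimed 5.00% over both looks instead gives 1 − 0.95 × 0.95 = 9.75%, which is much the same.
- The seven secondary endpoints of 6.2 alone, independent: 1 − 0.95^7 = 0.302, about 30%.
- The same seven with equicorrelated normal test statistics (400,000 simulated draws): 0.229 at correlation 0.5 and 0.148 at 0.8, about 23% and 15%. The correlations are assumed, not taken from the protocol.

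**The case against.** Much can be said for a milder reading, and most of it stands.

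*Subgroups.* A reader might infer that the ten factors of 21.5 are all confirmatory and quote 1 − 0.95^10 = 40%. The documents do not support this. The only link is one parenthesis at the end of a damaged passage, and 21.5 itself makes no such claim. The parenthesis needs clearing up, but it does not support a quantified error rate.

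*The singular.* It is tempting to say that the confirmatory variable is unidentified and then to charge the plan with 30%. Taken literally, the wording means one test, and the figure is 9.6%. Taken loosely, as the singular heading of 6.2 suggests, it means the whole list, and 30% is the independent-test upper illustration. Both belong in the range, and neither is the trial's established error rate.

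*Phase III.* Section 5 calls this a "Phase III single center trial". A reader might see a contradiction with the exploratory label, but the two terms are not formally exclusive. In 21.1 the word exploratory stands in the explanation of the sample size. The real tension is between exploratory and confirmatory.

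*The SAP.* Section 21 leaves complete details to a later SAP. One might infer that the SAP could only repair this by contradicting 21.3. That goes too far: a fixed sequence, with the primary first and then a named secondary endpoint, each at the full level, adjusts no p value and is arguably compatible. A Holm-type adjustment would conflict. Still, the protocol states a rule here rather than leaving one open.

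*Consequence.* The harm lies in future reporting, and the absence of adjustment is openly declared. That limits the seriousness of the point but does not remove it.

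**Conclusion.** The point holds as a defect of stated wording. Section 21.3 gives confirmatory status to secondary efficacy testing and refuses multiplicity adjustment for it. Section 21.1 describes the trial as exploratory, and the only error-rate guarantee, in 21.7, stops at the primary endpoint. No plausible filling of the gap in 21.3 removes this.

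The illustrated chance of a false confirmatory claim runs from about 9.6% (one secondary variable with the primary) to about 30% (seven secondary endpoints, independent), with 15% to 23% for the seven at the assumed correlations. All of these rest on the assumed 0.05 per secondary test and on no true effect.

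It does not follow that the primary test is compromised, or that the subgroups have been declared confirmatory. The change is worth making before the SAP is fixed.

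**What to change.** Replace the last two sentences of 21.3 with:

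> Only the primary endpoint of section 6.1 is tested confirmatorily, at the level set in 21.7. All secondary and subgroup analyses are exploratory, are reported as estimates with 95% confidence intervals without multiplicity adjustment, and are not presented as confirmatory evidence.

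This also disposes of the stray parenthesis about subgroups. In 21.1, limit the word exploratory to the basis of the sample size.

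If a confirmatory secondary claim is wanted, name the endpoint and its time point and test it only after the primary endpoint is significant. Use a fixed sequence for an ordered choice, or Holm if several endpoints are named, at a total level no higher than that used for the primary endpoint at the same analysis. The gate matters: under no true effect and independence, Holm at 0.05 across seven secondary endpoints run beside an ungated primary test at 0.05 gives 1 − 0.95 × (1 − 0.05/7)^7 = 9.6%.

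The cost is protocol wording, and secondary and subgroup results can no longer be presented as confirmed outside that procedure. No analysis is lost.

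Two neighbouring inconsistencies are separate points to reconcile. Section 21.7 sets its boundary "for the primary endpoint (one-year stroke or death"), whereas 6.1 defines the primary endpoint as "All strokes & death within 30 days post-surgery and ipsilateral hemorrhage afterwards". Section 6.2 uses a 1-year window for contralateral infarction and treated-side TIA, where the synopsis gives 2 years.
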